8.4.1. Time Period and Frequency for Collecting AE and SAE Information

AEs, ADEs, SAEs and SADEs will be collected from signing of the ICF at baseline (V1) and until Week 4 (pilot phase) or Week 12 (pivotal phase), respectively, at the timepoints specified in the SoA (see Section 1.3). Aes, ADEs, SAEs and SADEs are followed until they have reached a final outcome or the subject's participation in the clinical investigation ends, whichever comes first.

All SAEs and SADEs will be recorded and reported to the sponsor immediately and under no circumstance should this exceed 24 hours after SAE / SADE awareness. The investigator or designee will submit any updated SAE/SADE data to the sponsor within 48 hours of it being available. For all reportable events, the sponsor will adhere to local reporting timelines.

Information on relevant AEs, ADEs, SAEs, and SADEs must be entered in the CRF.

Investigators are not obligated to actively seek information on AEs, ADEs, SAEs, or SADEs after conclusion of the clinical investigation participation. However, if the investigator learns of any SAE or SADE, including a death, at any time after a subject has been discharged from the clinical investigation, and he/she considers the event to be reasonably related to the intervention or participation in the clinical investigation, the investigator must promptly notify the sponsor regardless of the time that has elapsed (post-clinical investigation events).

8.4.2. Method of Detecting AEs, ADEs SAEs, and SADEs

Care will be taken not to introduce bias when detecting AEs, ADEs, SAEs, and/or SADEs. Open-ended and nonleading verbal questioning of the subject is the preferred method to inquire about AE occurrences.

8.4.3. Follow-up of AEs, ADEs SAEs, and SADEs

After the initial AE/ADE/SAE/SADE report, the investigator is required to proactively follow each subject at subsequent visits/contacts. All SAEs and SADEs will be followed until resolution, stabilization, the event is otherwise explained, or the subject is lost to follow-up (see Section 7.3).

8.4.4. Regulatory Reporting Requirements for reportable events

- Prompt notification within 24 hours of SAE/SADE awareness by the investigator to the sponsor of a SAE/SADE is essential so that legal obligations and ethical responsibilities towards the safety of subjects and the safety of the IMP under clinical investigation are met.
- The sponsor has a legal responsibility to notify relevant regulatory authorities about the safety of the intervention under clinical investigation. The sponsor will comply with country-specific regulatory requirements relating to safety reporting to the regulatory authority, institutional review board (IRB)s, and investigators.
- An investigator who receives an investigator safety report describing a SAE/SADE or other specific safety information (e.g., summary or listing of SAEs/SADEs) from the sponsor will review and then file it in the investigator site file and will notify the IRB, if appropriate according to local requirements.

8.5. Reporting of Device deficiencies

The definition for device deficiencies can be found in Section 10.2.6. Device deficiencies will be collected from start of dCBT-PF use and until Week 4 (pilot phase) or Week 9 (pivotal phase). Device deficiencies will be reported by the subject or the site.

Device deficiencies can only occur in the dCBT-PF group.

Device deficiency that might have led to a serious adverse event if appropriate action had not been taken, intervention had not occurred, or circumstances had been less fortunate must be reported to the sponsor within 24 hours of device deficiency awareness. The sponsor will report this type of device deficiencies to the regulatory authority, if required, institutional review board (IRB)s, and investigators. This will be according to national legislation.

[figure not shown]

9. Statistical Considerations

The statistical analysis plan will be finalized prior to enrolling the first subject in the pivotal phase of the clinical investigation, and it will include a more technical and detailed description of the statistical analyses described in this section. This section is a summary of the planned statistical analyses of the most important endpoints including primary and key secondary endpoints.

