2.3.3. Overall Benefit Risk Conclusion

The overall benefit risk balance is considered positive. This is based on the consideration that none, or a limited number of, ADEs are expected using dCBT, the virtual nature of the clinical investigation and potential benefits in treating anxiety with dCBT.

3. Objectives, Endpoints, and Estimands

[figure not shown]
Pilot investigation – Part 1:

Objectives	Endpoints
Primary	
To evaluate the functionality of dCBT-PF in patients with IPF	Subjects feedback on functionality and experience of the dCBT-PF at Week 4
Safety	
To evaluate the safety of dCBT-PF in patients with IPF	AEs, ADEs, SAEs, SADE and device deficiencies which could lead to an ADE or SADE

Pivotal investigation – Part 2:

Objectives	Endpoints
Primary	
To evaluate the efficacy of dCBT-PF versus control on patient-reported anxiety symptoms in patients with PF	Change from baseline in anxiety symptom severity assessed by GAD-7 at Week 9
Key secondary	
To evaluate the efficacy of dCBT-PF versus control on clinician-reported anxiety symptoms in patients with PF	Change from baseline in anxiety symptom severity as assessed by Hamilton anxiety rating scale (HAM-A) at Week 9
To evaluate the efficacy of dCBT-PF versus control on patient-reported health-related quality of life (HRQoL) in patients	Change from baseline in HRQoL assessed by K-BILD psychological domain score at Week 9
with PF	Change from baseline in HRQoL assessed by K-BILD total score at Week 9

Safety	
To evaluate the safety of dCBT-PF versus control in patients with PF	AEs, ADEs, SAEs, SADEs and device deficiencies which could lead to an ADE or SADE

Primary Estimand:

The change from baseline to Week 9 in GAD-7 scores, assessed for the intention-to-treat population with treatment as randomised, independent of treatment withdrawal or major deviations according to the treatment policy, with withdrawals from the clinical investigation prior to Week 9 not possible to follow-up being imputed using multiple imputation including their last known assessment. The difference between treatments with 95% confidence intervals from ANCOVA adjusting for stratification will be estimated.

Key Secondary Estimands:

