The planned dCBT-PF treatment duration is 9 weeks with an intended daily use of 10 minutes. Traditional CBT conducted via sessions with a psychologist, or a psychotherapist can vary considerably in length and duration, with sessions lasting between 30 to 60 minutes and treatment containing 5 to 20 sessions (NHS, 2019). The dCBT-PF consist of 7 interventional CBT modules (Therapy modules) and 3 non-interventional modules (PF Essentials). A target treatment duration of 9 weeks in the pivotal part of the clinical investigation is considered justifiable based on both traditional and digital CBT experience.

To minimize bias, the clinical investigation will have a randomised, assessor-blind, controlled design. Subjects will be randomised 1:1 to dCBT-PF or an open-label waitlist control group and the randomization will be stratified by self-reported anxiety severity based on GAD-7 score to ensure an equal distribution in both groups (active and control).

Implementation of a placebo-app (sham) would not provide sufficient blinding and was considered to create substantial bias in the design of the clinical investigation. A clinician-reported outcome, HAM-A, assessed by a blinded clinician, is implemented to support the primary endpoint.

The proportion of PF patients with mild to moderate anxiety (scoring 5-14 on a 0-21 scale) may be as high as 60% in patients with PF (Coelho et al., 2010; Glaspole et al., 2017; Holland et al., 2014; Lee et al., 2017). Although live sessions with a psychotherapist providing traditional CBT could be effective for PF patients, psychological therapy or other mental health interventions are not part of standard of care in patients with PF (Raghu et al., 2015).

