4.3. End of Clinical Investigation Definition

End of clinical investigation is defined as the date of the last visit of the last subject. A subject is considered to have completed the clinical investigation if he/she has completed the Week 12 visit (follow-up).

5. Investigation Population

Part 1 of this clinical investigation will enroll adult subjects with IPF and mild to severe anxiety (i.e., a GAD-7 score \geq 5).

Part 2 will enroll adult subjects with PF and mild to severe anxiety (i.e., GAD-7 score \geq 5).

Prospective approval of deviations to recruitment and enrollment criteria, also known as waivers or exemptions, is not permitted.

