6.2. Preparation, Handling, Storage, and Accountability

Subjects randomised to the dCBT-PF will receive a unique product code. This product code gives access to the dCBT-PF. Subjects will download an app and use the dCBT-PF on their own mobile or tablet device.

Subjects will receive instructions on how to download the dCBT-PF app from written instructions and/or via a virtual onboarding session with the site staff.

Access to the dCBT-PF will be revoked after the subject has completed the clinical investigation.

The number of days the dCBT-PF has been accessed, the time spent, and the number of modules completed will be logged in the dCBT-PF system and will be transferred to the database for the clinical investigation.

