9.3.4. Safety Analyses

Safety analysis will be based on the safety set.

AEs will be analyzed using quantitative and qualitative measures. AEs will be summarized by treatment group for all AEs, ADEs, SAEs, SADEs (unanticipated SADE (USADE), or anticipated SADE (ASADE)), deaths, AEs leading to discontinuation of dCBT-PF or to withdrawal from investigation, and device deficiencies. AEs will be coded using the Medical Dictionary for Regulatory Activities (MedDRA) and summarized by system organ class and preferred term for each treatment group. ADEs and SADEs only applies to the dCBT-PF therapy group.

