10.2.6. Device deficiencies

Device deficiency definition

Device deficiency is inadequacy of a medical device with respect to its identity, quality, durability, reliability, usability, safety, or performance.

Device deficiencies include:

- Malfunctions (failure to perform in accordance with its intended purpose when used according to instructions)
- Use errors (inability of user to use the device properly, which user might be aware or unaware about)
- Inadequacy in the information supplied by manufacturer including labelling related to investigational medical device or the comparator

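### Pivotal device-deficiency collection stops at Week 9, but active-arm subjects keep the app until after the Week 12 visit

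*Combined protocol and SAP*

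**What the plan says.** Section 8.5 sets the collection window: "Device deficiencies will be collected from start of dCBT-PF use and until Week 4 (pilot phase) or Week 9 (pivotal phase"). The same section adds a duty for deficiencies that might have led to a serious adverse event: these "must be reported to the sponsor within 24 hours of device deficiency awareness". That duty runs from awareness and has no calendar end.

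App access follows a different rule. Section 6.2 says "Access to the dCBT-PF will be revoked after the subject has completed the clinical investigation", and Section 4.3 says "A subject is considered to have completed the clinical investigation if he/she has completed the Week 12 visit (follow-up").

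Week 9 comes from the treatment plan. Section 4.2 states "The planned dCBT-PF treatment duration is 9 weeks with an intended daily use of 10 minutes", and Table 2 in Section 1.3 labels V4 (Week 9) as end of treatment.

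The pivotal safety endpoint in Section 3 is "AEs, ADEs, SAEs, SADEs and device deficiencies which could lead to an ADE or SADE". Section 9.3.4 lists what will be summarised by treatment group, ending with "AEs leading to discontinuation of dCBT-PF or to withdrawal from investigation, and device deficiencies". Section 10.2.6 defines a deficiency without requiring that an adverse event occurred. One listed type is "Use errors (inability of user to use the device properly, which user might be aware or unaware about").

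**The concern.** A deficiency can arise for as long as the subject can open the app. The plan stops looking at Week 9 but leaves the app open to Week 12. Adverse events, adverse device effects and their serious forms are all collected to Week 12 (Section 8.4.1), so one component of the safety endpoint closes three weeks before the others.

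The 24-hour duty does not fill the gap, because its threshold is a possible serious adverse event. The endpoint is wider: it also takes in deficiencies that could lead to a non-serious adverse device effect.

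What is at stake is the completeness of the deficiency summary under Section 9.3.4, not the efficacy result.

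**Working it through.** The plan states no figure to reproduce beyond the visit days, so the check is calendar arithmetic followed by a comparison of provisions.

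**Inputs**
- V4, Week 9: Day 64 ±7 days (Section 1.3, Table 2)
- V5, Week 12: Day 85 ±3 days (Table 2)
- Treatment start: Day 1 (Table 2)
- Maximum enrolment: 250, randomised 1:1 (Section 1.1)

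**Visit days.** 9 × 7 + 1 = 64 and 12 × 7 + 1 = 85, which agree with Table 2.

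**Length of the gap for a subject who completes**
- Nominal: 85 − 64 = 21 days
- Shortest within visit windows: (85 − 3) − (64 + 7) = 82 − 71 = 11 days
- Longest within visit windows: (85 + 3) − (64 − 7) = 88 − 57 = 31 days

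**Share of the access period.** Nominal access is 85 − 1 = 84 days, and 21 / 84 = 0.25, or 25%. This is a share of days with access, not of use.

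**Upper bound on access time outside the window.** 250 / 2 = 125 active subjects, and 125 × 21 = 2,625 subject-days (2,625 / 365.25 ≈ 7.2 subject-years). This assumes full enrolment and no withdrawal.

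**Does another provision close the gap?**

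| Provision | Reach after Week 9 | What it leaves out |
|---|---|---|
| 8.4.1 and 10.2.2: adverse device effects, including those from malfunction or use error, to Week 12 | Deficiencies that caused an event | Deficiencies without an event |
| 8.5: 24-hour duty | Deficiencies that might have led to a serious adverse event | Deficiencies below that level |
| 10.2.5: deficiency collection | Gives a start and no end | Does not override the explicit Week 9 limit in 8.5 |
| 10.2.5: open question at each visit | Could bring an app problem to light at V5 | Is framed as an adverse-event question and does not require a deficiency to be recorded |
| 7.1 and 7.2: device discontinuation, withdrawal | Ends use for those subjects | Subjects who stay on the device and complete |
| 7.1.1: restart after a temporary stop only within the treatment period | Limits restarts | Does not close access for anyone else |

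The residue is event-free deficiencies below the level of a serious near miss, in active-arm subjects, between the Week 9 and Week 12 visits.

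**Who is not affected.** In the pilot, collection and the last visit both fall at Week 4. Control subjects receive the app only after Week 12, outside the scope of this plan (Section 6.5).

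**The case against.** The strongest reply is that Week 9 is a deliberate and coherent limit. Treatment is planned for 9 weeks, subjects are instructed to use the app for that time, and adherence and concomitant medication also stop at V4 in Table 2. Section 7.1.1 suggests that use is not meant to run into follow-up. On this reading Section 6.2 is only an accountability rule: access is not exposure, and none of the instructed use falls outside the window. Most of the safety content is caught elsewhere, and Section 2.3.1 anticipates one residual risk, negative wellbeing or distress, which is collected as an adverse event to Week 12.

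Much of this stands, and it is why the point is minor. It explains the date but does not reconcile it with the access rule: the plan neither ends access at Week 9 nor watches for deficiencies until access ends. Later use is also plausible. Section 6.1 ties the 9 weeks to use as intended and calls the period an estimate, while pivotal subjects are to complete all modules. Section 6.4 provides for compliance below expectation. A subject who is behind could carry on while the app is open. How many would do so is not known.

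One limit of the check should be stated. The dCBT-PF / control row of Table 2 could not be read reliably in the available text, the schema in Section 1.2 was not visible, and neither was any text for Section 8.6. None of these was relied on. The finding rests on the explicit sentences in Sections 8.5, 6.2 and 4.3.

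**Conclusion.** The concern holds, as a minor gap in safety capture. Followed as written, the plan does not require a deficiency after Week 9 to be collected if it caused no event and could have led only to a non-serious adverse device effect. Such a deficiency nevertheless belongs to the stated safety endpoint, and the subject still has the device.

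The window is 21 days nominally (11 to 31 with visit windows) for active-arm subjects who complete. This assumes that access runs as Sections 6.2 and 4.3 say and that Week 9 in Section 8.5 means the V4 visit. The number of missed deficiencies cannot be estimated, because the documents give neither a deficiency rate nor expected use after Week 9. The primary and key secondary analyses at Week 9 are not touched.

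**What to change.** In Section 8.5, with matching text in Section 10.2.5, set the pivotal window as *from start of dCBT-PF use until access to dCBT-PF is revoked*. At V5, ask active-arm subjects about device problems alongside the adverse-event and adverse-device-effect inquiry already scheduled there. Section 6.2 gives no date for revocation beyond completion and V5 is the last contact, so it should also say that access ends at the V5 visit; otherwise the new wording leaves a short tail.

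The cost is a phrase in each of the sections named and one more question for active-arm subjects at an existing contact. There is no new visit and no effect on sample size, the primary analysis or the testing order.

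If the sponsor means use to stop at Week 9, revoking access at V4 in Section 6.2 would also align the rules. That changes what subjects can do during follow-up, whereas extending collection changes only what is recorded.

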9.1. Statistical Hypotheses

The aim of this clinical investigation is to show superiority of dCBT-PF over a control group regarding selected efficacy measures. The null hypothesis to be tested for each endpoint will be that there is no difference between dCBT-PF and control, against the alternative hypothesis that dCBT-PF is better than control. All tests will be done using 2-sided alternatives.

9.2. Analysis Sets

For the purposes of analysis, the following analysis set has been defined:

Subject Analysis Set	Description	
Intention to treat (ITT) analysis set	All randomised subjects. Subjects will be included in the analyses according to the intervention they were randomised to.	
Safety set	All enrolled subjects. Subjects will be analyzed according to the actual intervention received, dCBT-PF or control.	

9.3. Statistical Analyses

9.3.1. General Considerations

All tests will be 2-sided at a 5% significance level.

Baseline will be defined as the last non-missing assessment obtained prior to randomization.

Stratification will be done based on baseline disease severity defined as the total score on the GAD-7 questionnaire (GAD-7 score 5-9, 10-14 or ≥15 points) at baseline (Visit 1).

The actual stratification will be used as factors in the statistical analysis, subjects included in wrong stratum at randomization will be moved to their correct strata belonging in the analyses.

Continuous variables will be summarized using (arithmetic) means, standard deviation (SD), median, minimum, and maximum value, categorical variables will be summarized using numbers and percentages.

The ITT analysis set is used for the main analysis of all endpoints related to the efficacy objectives. Sensitivity analyses related to efficacy objectives will be described in the SAP. The safety analysis set is used to analyze the endpoints and assessments related to safety.

All data regarding subject characteristics, efficacy and safety will be listed.

9.3.2. Primary Endpoint/Estimand Analysis

The primary endpoint, change from baseline in patient-reported anxiety symptom severity assessed by GAD-7 at Week 9, will be compared between treatment groups using an ANCOVA model with treatment and strata (baseline anxiety severity) as factors, the baseline GAD-7 score as covariate and the baseline by strata interaction.

The adjusted mean difference between groups will be given together with 95% confidence intervals and associated 2-sided p-value.

Withdrawals prior to Week 9 not possible to follow-up will be imputed using multiple imputation taking subjects baseline characteristics, treatment, and post-treatment GAD-7 scores into account.

The ITT analysis set will be used for the main analysis of the primary endpoint. Sensitivity analyses will be performed with alternative methods for imputation (for instance using the average of the opposite treatment group as base) and a tipping point analysis will also be performed investigating the impact on the treatment effect by successive shifts introduced in the imputation for the active group. Sensitivity analysis will be described in the SAP. In all analyses subjects will be included as randomised. All collected data post-intervention will be used to assess the endpoint.

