6.3. Measures to Minimize Bias: Randomization

This is a randomised, assessor-blind, controlled, parallel-group, clinical investigation. Subjects, care providers, investigators, sponsor, and CRO/vendor staff know if the subject is randomised to dCBT-PF or the control group. The control group is implemented to serve as a baseline for determining the effectiveness of the intervention. The control group will not receive any treatment but will follow the same assessment as the group randomised to dCBT-PF. Subjects in the control group will receive access to dCBT-PF treatment after the follow-up visit at Week 12 (see Section 6.5).

The clinician assessing rating anxiety based on the HAM-A questionnaire will be blinded to treatment to reduce reporter bias.

Randomization will be stratified by: Anxiety severity (GAD-7 score 5-9, 10-14 or >15 points) at baseline to prevent imbalance in anxiety level between the dCBT-PF and control group.

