6.6. Prior and Concomitant Therapy

Concomitant therapy is defined as any therapy (including over-the-counter, prescription medicines, oxygen supplementation, recreational drugs, vitamins, treatment from a psychologist or psychiatrist and/or herbal supplements) or other specific categories of interest that the subject is receiving or continues at the time of enrollment or receives after start of treatment with the dCBT-PF.

All concomitant therapy taken according to the subject at baseline (Visit 1) should be recorded. In addition, relevant prior therapy taken up to 4 weeks prior to baseline (Visit 1) should be recorded. Relevant prior therapy is defined as antifibrotic treatment, psychological therapy including counseling, antidepressants, or anti-anxiety treatments. Other relevant prior therapy can be reported at investigator's discretion.

Concomitant therapy and prior therapy must be recorded along with:

- Reason for use
- Dates of administration including start and end dates
- Dosage information including dose and frequency

7. Discontinuation of Investigational Medical Device and Subject Discontinuation/Withdrawal

Discontinuation of the clinical investigation is detailed in Appendix 1 (see Section 10.1).

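### The tipping-point analysis in section 9.3.2 shifts imputed GAD-7 values in the active arm only, so it cannot show how far the primary result depends on missing waitlist controls

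*Combined protocol and SAP*

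**What the plan says.** Section 9.3.2 makes multiple imputation the main handling of missing Week 9 GAD-7 scores: "Withdrawals prior to Week 9 not possible to follow-up will be imputed using multiple imputation". This applies to both arms. Two kinds of sensitivity analysis follow. One uses alternative imputation methods, "for instance using the average of the opposite treatment group as base". The other is a tipping-point analysis "investigating the impact on the treatment effect by successive shifts introduced in the imputation for the active group". The section does not say which arm or arms the opposite-group average applies to, and it names no shift for controls. It then defers the detail: "Sensitivity analysis will be described in the SAP".

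The control arm can have missing data too. Under section 4.2, "Subjects will be randomised 1:1 to dCBT-PF or an open-label waitlist control group". Under section 6.3, "The control group will not receive any treatment but will follow the same assessment as the group randomised to dCBT-PF". Section 7.2 lets any subject withdraw, and also has subjects withdrawn for significant new or worsened distress, without limiting this to one arm.

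**The concern.** A tipping-point analysis asks how wrong the imputation must be before the conclusion changes. The difference between arms depends on the imputed values in both. If only active values move, the control imputation is taken as correct throughout, and no step of the analysis questions it.

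This matters because the primary outcome is self-reported and allocation is open. If missing controls did better at Week 9 than the imputation assumes, the benefit of dCBT-PF would be overstated, and no active-arm shift represents that error directly. If few active values are missing, the tipping shift could be reported as implausibly large although a smaller error among controls, or in both arms together, would remove significance.

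**Working it through.** The readable text states no tipping value, effect, SD, power or dropout by arm, so there is no planned figure to reproduce.

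**Inputs from the documents**
- Test level: "All tests will be 2-sided at a 5% significance level" (section 9.3.1), hence the multiplier 1.96.
- At most 250 subjects, allocated 1:1 (section 4.1), hence at most 125 per arm.
- GAD-7 range 0-21 (section 8.2.1).

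**Assumptions**
- Base case: difference d = 2 points, SD = 4. Range: d = 1.5 to 2.5, SD = 4 to 5.
- Missing share: pA on active, pC on control, varied below.

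**Formulas.** Let dA be the upward (worse) shift of imputed active values and dC the downward (better) shift of imputed control values.
- Loss of estimated benefit = pA × dA + pC × dC. The protocol's analysis sets dC = 0.
- SE = SD × √[1/(125(1 − pA)) + 1/(125(1 − pC))], held fixed under the shifts as an approximation.
- Margin before significance is lost: M = d − 1.96 × SE.
- Tipping shifts: M/pA (active only), M/pC (control only), M/(pA + pC) (equal and opposing in both arms).
- Ratio of active-only to equal-opposing shift = (pA + pC)/pA = 1 + pC/pA, whatever d and SD are.

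**Worked case, 5% active and 20% control missing.** SE = 4 × √(1/118.75 + 1/100) = 0.543. M = 2 − 1.96 × 0.543 = 0.936. Active only: 0.936/0.05 = 18.7. Control only: 0.936/0.20 = 4.7. Equal opposing: 0.936/0.25 = 3.7.

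| Missing, active / control | M | Active only | Control only | Equal opposing | 1 + pC/pA |
|---|---|---|---|---|---|
| 5% / 20% | 0.94 | 18.7 | 4.7 | 3.7 | 5.0 |
| 10% / 20% | 0.92 | 9.2 | 4.6 | 3.1 | 3.0 |
| 15% / 15% | 0.92 | 6.2 | 6.2 | 3.1 | 2.0 |
| 20% / 10% | 0.92 | 4.6 | 9.2 | 3.1 | 1.5 |
| 25% / 10% | 0.90 | 3.6 | 9.0 | 2.6 | 1.4 |

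On a 0-21 scale, a mean shift of 18.7 points is possible only if the imputed active mean is at or below 21 − 18.7 = 2.3.

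**Range over d = 1.5 to 2.5 and SD = 4 to 5** (active only against equal opposing):
- 5% / 20%: 3.4 to 28.7 against 0.7 to 5.7.
- 15% / 15%: 1.0 to 9.5 against 0.5 to 4.7.
- 20% / 10%: 0.8 to 7.1 against 0.5 to 4.7.

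**Simulation check.** Sixty trials per scenario were run with 20 imputations, Rubin's rules and the protocol's ANCOVA (d = 2, SD = 4, shifted values not truncated). Median tipping shifts among significant trials, as active only / control only / both:
- 5% / 20%: 18.75 / 5.5 / 4.5. In 33% of significant trials the active-only shift never tipped within 21 points.
- 15% / 15%: 6.25 / 6.25 / 3.5.
- 20% / 10%: 4.5 / 8.5 / 3.0.

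**Opposite-group average.** Applied to missing controls, it moves them by about d, so the benefit becomes d × (1 − pC).
- 5% / 20%, d = 2, SD = 4: 2 × 0.80 = 1.60, and the upper 95% limit of the difference is −1.60 + 1.06 = −0.54. The result stays significant, although a control shift of 4.7 would overturn it.
- 5% / 20%, d = 1.5, SD = 5: 1.5 × 0.80 = 1.20, and the limit is −1.20 + 1.33 = +0.13. Here this analysis does expose the fragility.

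**The case against.** The strongest reply has four parts.

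- **Section 9 is a summary.** It says so itself and leaves sensitivity detail to the SAP, whose text cannot be read here. A reader might infer that the SAP omits a control shift, but that can be neither confirmed nor excluded. What stands is that the protocol names one arm, and its sentence would need aligning even if the SAP already covers both.
- **Controls are not wholly untested.** The opposite-group average, if applied to controls, moves them in the direction at issue and can reveal a fragile result. But it is only an example, its arms are not stated, and one fixed scenario does not locate a tipping point.
- **The planned arm may be the stricter one.** Only active subjects carry the daily app use (section 6.1), and section 2.3.1 names distress after starting CBT as a risk. Controls have reasons to stay: payment on completion (section 5.5) and later access to the app (section 6.5). At 20% active and 10% control missing, active-only tips at 4.6 and control-only at 9.2. This stands in full, although equal opposing shifts still tip sooner, at 3.1.
- **Equal opposing shifts move two quantities.** A shift of 3.7 in each arm is 7.4 points of combined movement, and the floor at 0 limits how far controls who entered at 5-9 can fall. This is fair. The control-only column is the cleaner one-arm comparison, and bounded shifts belong in the grid.

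A reader might also infer that controls will leave to seek treatment elsewhere and so score better than imputed. Section 6.6 does not show this. It lists "treatment from a psychologist or psychiatrist" as concomitant therapy to be recorded, and under the treatment-policy estimand such a subject can remain and be counted. Withdrawal for distress under section 7.2 could bias the other way, since those controls might score worse than imputed.

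**Conclusion.** The limitation is real and follows from the algebra: with the control shift fixed at zero, the planned analysis cannot measure dependence on missing controls. Whenever both arms have missing data, its tipping shift exceeds the equal-opposing figure by 1 + pC/pA. That factor is 2 or more only if control missingness equals or exceeds active missingness. In the base case it ranges from 5.0 (5% / 20%) to 1.4 (25% / 10%).

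It would be tempting to conclude that the plan will make a fragile result look robust. The documents do not support that. The effect, SD and missing shares above are all assumptions, and the direction of any departure among missing controls is unknown. Nor is there a faulty HAM-A tipping point to correct, because section 9.3.3 plans none. The point is a cheap and specific improvement to a sensitivity analysis. It is not evidence of bias in the primary estimate.

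**What to change.** In section 9.3.2, and in the SAP if it is not already so:

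- Specify a two-dimensional tipping-point analysis for GAD-7, with independent shifts in each arm (imputed active values worse, imputed control values better), each starting from zero over a pre-specified grid.
- Keep shifted values within 0-21.
- Report the shift pairs at which the two-sided p-value crosses 0.05, with the missing share in each arm.
- State to which arm or arms the opposite-group-average imputation applies.

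The cost is about a sentence or two of text, a second loop in the analysis program and a longer output table. The robustness statement may also turn out less favourable. The grid should be fixed in advance, because section 6.3 says that the sponsor and CRO staff know the allocation. Extending it to HAM-A, within that scale's 0-56 range, is optional.
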